8.3 Handling of Missing or Incomplete Data

8.3.1 Missing Primary and Secondary Effectiveness Outcomes

For the primary and secondary effectiveness endpoints, the imputed values described in Sections 4.1.1 and 4.1.2 will be performed for the missing endpoints.

8.3.2 Partial Dates

For incomplete dates such as AE or medication start date or stop date, the imputed dates described in the table below will be used.

Imputation Rules for Partial Adverse Event or Concomitant Medication Start and Stop Dates

Date	Missing	Imputation	Exception
Start Date	Day	01	Default to Study Day 0 (day of first injection procedure) if an event starts in the same year and month as Study Day 0
	Day/Month	01Jan	Default to Study Day 0 if an event starts in the same year as Day 0
Stop Date	Day	Last day of the month	Default to the End of Study Date if the imputed event stop date is after the End of Study Date or before start day of the event
	Day/Month	31DEC	

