4.0 STUDY ENDPOINTS

4.1 Effectiveness Endpoints

4.1.1 Primary Effectiveness Endpoint

The primary effectiveness endpoint is the change in medication-free mean diurnal IOP from baseline at 12 months (i.e. medication-free mean diurnal IOP at 12 months – medication-free mean diurnal IOP at baseline). The medication-free mean diurnal IOP (i.e. average of three medication-free IOP's measured at three different time points) will be calculated for each subject. For each subject, a negative change in mean diurnal IOP value means a reduction; a positive value means an increase.

Criteria for Failure to Respond

The medication-free mean diurnal IOP at 12 months will be imputed for subjects who meet the following criteria:

- IOP persistently below 6mmHg (defined as an intraocular pressure below 6mmHg that is present on two consecutive follow-up visits after the three month visit),
- underwent secondary IOP lowering interventions to control IOP (e.g., laser trabeculoplasty, trabeculectomy, shunt or valve placement, iridotomy/iridectomy) prior to the 12-month visit,
- post-operative introduction of an oral carbonic anhydrase inhibitor,¹
- no diurnal IOP data collected from the available Month 12 visit,
- underwent other secondary surgical interventions (SSI) that could affect IOP, or
- use of ocular hypotensive medication within 4 weeks of the Month 12 washout visit²

¹ Does not include use in the perioperative period

² If the study subject fails to remember not to use ocular hypotensive medication for the study eye per the required washout period prior to this visit, they can be reinstated to washout and return for a 12 month washout IOP visit as long as it falls within the specified visit window.

For subjects who meet any of the criteria above, the medication-free mean diurnal IOP at 12 months will be imputed by the mean washout (i.e. medication-free) diurnal IOP at baseline.

It is expected that the follow-up rate will be better than 90% at 12 months postoperatively. Therefore, the primary analyses for the primary and secondary effectiveness endpoints will be based on the available medication-free mean diurnal IOP data at 12 months with the imputation described above. For sensitivity analyses, imputations of the missing 12-month medication-free diurnal IOP will be performed for the subjects that do not meet the criteria above and are discontinued prior to the 12-month visit (Section 9.4.3).

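### SAP 8.3.2 imputes partial start dates without checking them against the recorded stop, so pre-procedure events and drugs can be dated to Day 0; if imputed dates also feed the 4-week washout criterion, completed Month 12 washouts can be scored as failures

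*SAP*

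**What the plan says.** SAP 8.3.2 has one table for adverse events and medications: "For incomplete dates such as AE or medication start date or stop date, the imputed dates described in the table below will be used". No visible text exempts ocular hypotensive drugs.

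- **Start, day missing:** first of the month, except "Default to Study Day 0 (day of first injection procedure) if an event starts in the same year and month as Study Day 0".
- **Start, day and month missing:** 1 January, except "Default to Study Day 0 if an event starts in the same year as Day 0".
- **Stop, day missing:** "Last day of the month", unless this exception applies (end omitted): "Default to the End of Study Date if the imputed event stop date is after the End of Study Date or before start day of".
- **Stop, day and month missing:** 31 December.

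SAP 8.3.4 rules out other imputation for safety outcomes but keeps 8.3.2 and 8.3.3 in force. SAP 9.5.1 classifies events as intraoperative or postoperative.

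SAP 4.1.1 lists as a failure criterion "use of ocular hypotensive medication within 4 weeks of the Month 12 washout visit". A subject who meets it has the 12-month medication-free diurnal IOP replaced by baseline, and is a non-responder under SAP 4.1.2.

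**The concern.** A date imputation should not contradict a date that was recorded. Here the start default looks only at the known part of the start. A stop date that proves the item ended before the procedure is ignored or, in one pattern, overwritten.

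For safety, an eye event that arose and resolved during the pre-procedure washout can acquire an onset on the day of VISCO360 or SLT. Such events can be recorded: subjects are enrolled at consent (Protocol 8.1), and only conditions already present at enrolment are exempt from recording (Protocol 10.0).

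For effectiveness, the stake depends on how the 4-week criterion is programmed. If imputed log dates are used, a subject with a valid medication-free measurement is given zero change and non-responder status. As the SAP does not settle this, two programmers could score the primary endpoint differently.

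**Working it through.** The plan gives no figure to reproduce. The check applies the SAP 8.3.2 table literally to assumed dates.

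**(a) Start moved past a known stop.** Day 0 = 20 Apr 2018. Event start recorded as Apr 2018, stop recorded as 8 Apr 2018. The start month matches Day 0, so the start becomes 20 Apr. That is 20 − 8 = 12 days after the event ended. The stop is complete, so it is not imputed and the record keeps a stop before its start.

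**(b) Day 0 to End of Study.** Day 0 = 20 Jun 2018, End of Study = Day 730 (19 Jun 2020). Drug start recorded as 2018, stop recorded as May 2018.

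- Start: the year matches, so 20 Jun 2018.
- Stop: month end, 31 May 2018, which precedes that start, so 19 Jun 2020.

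A drug stopped at least 20 days before the procedure is shown as in use through the whole Month 12 window (Day 330–420).

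For a year-only start in the Day 0 year and a day-missing stop 28, 35 or 42 days before Day 0 in that year, there are 337 + 330 + 323 = 990 date combinations. In 961 (97%) the stop goes to End of Study.

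Other patterns, with the same Day 0, do not:

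| Recorded start | Recorded stop | Result |
|---|---|---|
| Jun 2018 | Jun 2018 | 20–30 Jun 2018 (Day 0–10) |
| Mar 2018 | May 2018 | stays pre-procedure |
| 2017 | May 2018 | stays pre-procedure |
| 2018 | 2018 | Day 0 to 31 Dec 2018 |
| 2018 | 10 May 2018 | stop kept, 41 days before start |

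**(c) Month-end stop and the 4-week criterion.** Inputs: 4 weeks = 28 days (SAP 4.1.1); maximum washout 6 weeks = 42 days (Protocol 8.7), taken here to apply at Month 12 too.

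Example, Day 0 = 20 Jun 2018: true stop 10 May 2019, recorded May 2019, washout visit 18 Jun 2019 (Day 363). True gap: 39 days. Imputed stop: 31 May. Imputed gap: 18 days, below 28, so the criterion is met.

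In general, for a true gap of g days, the imputed gap is g minus the days left in the month. It falls below 28 unless the stop was in the last g − 27 days of its month. With stop days uniform over a 365-day year, and g from 28 to 42:

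share wrongly failed = [365 − 12 × (g − 27)] / 365

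- g = 28: (365 − 12)/365 = 353/365 = 97%
- g = 35: (365 − 96)/365 = 269/365 = 74%
- g = 42: (365 − 180)/365 = 185/365 = 51%

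The average over g = 28 to 42 is also 74%. No record is wrongly failed at 58 days or more. Counting exactly 28 days as within the window gives 100%, 77% and 54%. These shares apply only to records whose stop lacks a day.

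**Illustration of scale.** The documents give no partial-date rate and no share needing washout at Month 12. Assume 2–10% of stops lack a day and 30–60% of subjects need washout:

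- Low: 134 × 0.30 × 0.02 × 0.74 = 0.6 subjects per arm
- High: 134 × 0.60 × 0.10 × 0.74 = 5.9 subjects per arm

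**The case against.** The strongest reply is that the link to the endpoint is not in the documents. Medication status is handled at visits: only medication-free subjects have diurnal IOP at the Month 12 visit and others return after washout (Protocol 8.9); a missed washout can be repeated within the window (SAP 4.1.1, Protocol 8.7); a subject who cannot be washed out goes to masked Medical Monitor review (Protocol 8.7 and 13.0); and changes are recorded by visit (Protocol 8.8). Day-missing washout stops may be few. All of this stands, and is why (c) is conditional. Parts of SAP 9.4 are blacked out and could not be checked.

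Also, some drugs have 5- or 14-day minimum washouts (Protocol Table 1). At those gaps the 4-week criterion is met even with complete dates, so imputation adds no error. Those passages need separate reconciliation.

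On safety, one can say that Day 0 is a deliberate worst case, like the defaults for severity and relationship in SAP 8.3.3. That justifies Day 0 when the timing is unknown, but not when the recorded stop shows the event was over.

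Four stronger readings are tempting but not supported:

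- **An oral carbonic anhydrase inhibitor started months later, recorded by year only, escapes the failure criterion.** Its start would move to Day 0, and the footnote says "Does not include use in the perioperative period". But that period is undefined, and continued use is not perioperative merely because its start was imputed.
- **Each affected subject's responder status is wrong.** A subject going from 25 to 21 mmHg has a 16% reduction and is already a non-responder. Only the change is then wrong.
- **A definite bias favours VISCO360.** With 30% versus 60% needing washout and a 5.5 mmHg change in both arms, the arithmetic is 5.5 × 0.30 × 0.74 × (0.02 to 0.10) = 0.02 to 0.12 mmHg. The imbalance and rates are assumptions, and the 5.5 mmHg comes from SLT eyes without added medication, whereas the affected subjects are on drops.
- **The reference to an injection procedure leaves Day 0 undefined.** SAP 8.2.3 and 8.2.4 define it as the surgery or SLT day. The phrase is an editorial slip.

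**Conclusion.** The point holds in three parts of differing strength.

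- **(a)** Misdating to Day 0 follows directly from SAP 8.3.2 and, through SAP 8.3.4, reaches the safety outcomes without further assumption.
- **(b)** The run to End of Study also follows from the text, but only for a year-only start in the Day 0 year combined with a day-missing stop in an earlier month of that year.
- **(c)** The false Month 12 failure depends on imputed dates being used for SAP 4.1.1. Where they are, 97%, 74% and 51% of day-missing records are wrongly failed at true gaps of 28, 35 and 42 days, given uniform stop days, and a valid IOP is replaced by baseline. Under the same condition, a record of type (b) would also cover the washout window.

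The trial-level effect is probably small: roughly 1 to 6 subjects per arm under assumed rates. The case for change is that the stated rule can contradict recorded dates and leaves endpoint scoring open, and that both are cheap to close.

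**What to change.** Amend SAP 8.3.2 before database lock:

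1. Apply the Day 0 start default only if the recorded full or partial stop is missing or can fall on or after Day 0. Otherwise use the first day of the recorded month or year.
2. Where an imputed stop precedes an imputed start, correct the start. Do not default the stop to End of Study.
3. State that imputed dates are not used to score the SAP 4.1.1 failure criteria. Score them from the medication status recorded at the Month 12 or washout visit. Query partial hypotensive and oral carbonic anhydrase inhibitor dates before lock, and classify unresolved cases by masked review.

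The injection wording can be tidied in the same edit.

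The cost is a few lines of SAP text, some targeted date queries and a handful of masked classifications. No visits or subjects are added and no clinical rule changes.

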8.3.3 Missing AE Severity or Relationship to Surgical Procedure

The “severe” will be assigned to the missing AE severity level. The “definitely related” will be assigned to the missing AE relationship to the corresponding surgical procedure.

8.3.4 Safety Outcomes

No imputation will be performed for the safety outcomes other than the cases described in Sections 8.3.2 and 8.3.3.

8.4 Multiplicity Adjustment

The statistical tests for the primary and secondary effectiveness endpoints will be performed by the hierarchical approach (Section 4.1.2). The interim analyses specified in Section 5.1 are for safety data only. No other multiplicity adjustment will be performed.

9.0 STATISTICAL METHODS

9.1 General Principles of Data of Data Analyses

The primary effectiveness data analyses will be based on the mITT population. The effectiveness analyses based on the ITT and PP populations will also be performed. The safety data will be summarized based on the safety population.

The statistical analyses will be reported using summary tables and figures. Continuous variables will be summarized with means, standard deviations, medians, minimums, and maximums, and the number of non-missing observations for each study group. Other selected percentiles such as 25th and 75th percentiles may be presented. Categorical variables will be summarized by count and percentage of subjects in the corresponding categories.

9.2 Subject Enrollment and Disposition

9.2.1 Subject Disposition

Subject disposition will be summarized for all randomized subjects by the two study groups, VISCO360 versus Control (SLT) groups, separately. The summary will include the number and percentage (based on total number of subjects randomized) of subjects in each of the following categories:

- ITT population
- mITT population
- PP Population
- Safety population
- Available at 12 months
- Discontinued prior to the 12 months examination
- Discontinued prior to the 24 months examination
- Completed the 24 months examination

The number of subjects who are enrolled but not randomized will also be provided.

9.2.2 Subject Status by Study Visit

For the ITT population, PP population, and Safety population, subject accountability will be prepared based on Table A.1 of ISO 11979-7, 2006.

9.3 Demographics and Preoperative Characteristics

Subject demographics (age, race/ethnicity and gender) will be summarized by study group for the ITT, PP, and Safety populations using descriptive statistics. Age will be summarized as a continuous variable and categorized into the four groups based on the observed quartiles.

The baseline medicated IOP and washout (unmedicated) IOP will be summarized by study groups for the ITT and PP populations. They will be treated as continuous variables. Additionally, number and percentage of subjects will be presented for four unmedicated IOP groups based on the observed quartiles. For the four subgroups, the number of glaucoma medications in use at enrollment will be prepared for each of the study groups using descriptive statistics for categorical variables.

The above data summaries will be stratified by study site.

Medical and Ocular history will be summarized for each study group by number and percentage of subjects in the ITT population.

9.4 Effectiveness Endpoints Analyses

9.4.1 Primary Analysis for Primary Effectiveness Endpoint

The primary analysis of the primary effectiveness objective described in Section 4.1.1 will be based on the mITT population. The medication-free mean diurnal IOP change from baseline at 12 months will be calculated for each study eye. As described in Section 4.1.1, for subjects meeting the criteria listed in Section 4.1.1, their 12-month medication-free mean diurnal IOP will be imputed by the baseline medication-free diurnal IOP. In order to assess the pattern of the distribution, box-plots will be prepared for the medication-free mean diurnal IOP and its change from baseline for each of the two study groups.

The descriptive statistics (such as mean, standard deviation, median, minimum, and maximum) of the medication-free mean diurnal IOP and the change from baseline and the 95% confidence interval of the mean will be calculated for each of the two study groups. A two-sample t-test with a one-sided significance level of 0.025 will be used to test the statistical hypotheses described in Section 4.1.1. The two-sided 95% confidence interval based on the t-distribution will also be provided for the mean difference in the medication-free mean diurnal IOP between the two study groups.

9.4.2 Primary Analysis for Secondary Effectiveness Endpoint

The percent change in medication-free mean diurnal IOP from baseline at 12 months will be calculated for each study eye as follows:

$$\% \text{ change} = (12\text{-month medication-free mean diurnal IOP} - \text{baseline medication-free mean diurnal IOP}) \div (\text{baseline medication-free mean diurnal IOP}) \times 100\%.$$

Histograms of the percent change in medication-free mean diurnal IOP from baseline at 12 months will be prepared for the two study groups separately. The number and percent of subjects achieving $\geq 20\%$ reduction in medication-free mean diurnal IOP from baseline at 12 months (12-month IOP responder rate) will be calculated. The exact 95% confidence interval of the 12-month IOP responder rate will be calculated by the binomial distribution. For subjects who meet any of the criteria listed in Section 4.1 above, the non-responder (i.e. failure) will be imputed. An ones-side Fisher's exact test with a significance level of 0.025 will be used to compare the 12-month IOP responder rates between the two study groups. A 95% confidence interval of the difference in the 12-month IOP responder rate between the two study groups will be derived by the 2-sample normal distribution.

The image consists of a series of horizontal bars of varying lengths and positions. The bars are mostly black on a white background, with some white bars appearing in the middle section. The image is heavily processed, appearing as a binary or high-contrast representation of data. The bars are arranged in a staggered, non-uniform pattern across the frame.

The scatter plots of the 12-month medication-free mean diurnal IOP versus the baseline medication-free mean diurnal IOP along with a 45° line will be provided. The scatter plot of the percent change in medication-free mean diurnal IOP from baseline to 12 months versus the baseline medication-free mean diurnal IOP will also be provided. The Box plots of the change and percent change in medication-free mean diurnal IOP from baseline to 12 months will be prepared for each category of the covariates.

For the primary effectiveness endpoint, two-way ANOVA with study group, one of the factors listed above, and the interaction between the study group and the factor will be used to check the possible covariate effects. For the secondary effectiveness endpoints, the Gail-Simon test will be performed. A p-value of 0.15 will be used for evaluating the possible covariate effects. It should be noted that the subgroups of these covariates will be re-examined and may be re-categorized or eliminated due to small sample size (if there are < 10 subjects within each subgroup).

9.5 Safety Analysis

All safety analyses will be performed on the Safety population based on all available data

9.5.1 Adverse Event

Adverse events (AEs) will be classified as intraoperative or postoperative. The number and the percent of subjects reporting at least 1 adverse event of a given type will be summarized by study group. The corresponding 95% confidence interval of the percentage will be calculated by binomial distribution. Additionally, the number of reports and the proportion of events (the total number of events divided by the total number of subjects) of each type of AEs will be provided.

For each AE, the number and the percent of subjects reported with the event will be summarized by the severity level. For subjects with multiple reports of the same type of AE, the maximum severity will be used. Similarly, the AE relationship to the procedure will be summarized for the two study group separately. For subjects with multiple reports of the same type of AE, the closest relationship to the procedure will be used.

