	
compliance to elements of the study protocol (e.g., ophthalmic examinations, follow-up visits):
 
 a) inability to reliably complete visual field testing over the course of the study, b) uncontrolled systemic disease (e.g. diabetes, hypertension) that could compromise their participation in the study, c) disorders that pose a fall risk, as well as compromise ability to take a visual field exam and take glaucoma medications (e.g., Parkinson's disease), d) inability to discontinue use of blood thinners in accordance with surgeon's standard pre-operative and postoperative instructions, e) immunodeficiency concerns, f) other clinically significant ocular pathology other than glaucoma. 
21. Proliferative diabetic retinopathy 22. Previous surgery for retinal detachment 23. Central corneal thickness that is less than 450 microns or greater than 620 microns. 24. Clinically significant corneal dystrophy (e.g., bullous keratopathy, guttata, etc.) 25. Previous corneal surgery 26. Wet age-related macular degeneration 27. Clinically significant ocular inflammation or infection \leq 30 days prior to screening. 28. Participation in any clinical trial \leq 30 days prior to screening. 29. Women of childbearing potential if they are currently pregnant or intend to become pregnant during the study period; are breast-feeding; or are not in agreement to use adequate birth control methods to prevent pregnancy throughout the study. (A negative serum pregnancy test must be verified for females of child bearing potential). All women are considered to be of childbearing potential unless:
 
 A. Postmenopausal for at least 1 year OR B. Surgically sterile
STUDY DURATION	The primary safety and effectiveness endpoints will be evaluated when each study subject has a minimum of 12 months of post- follow-up data. All subjects will be followed through the 24-month time point.
SCHEDULE OF VISITS	1 day, 1 week, and 1, 3, 6, 12, 18, and 24 months

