6.2 SAFETY ENDPOINTS

- Best corrected visual acuity (BCVA) changes from baseline;
- Findings from pachymetry, slit lamp, fundus and gonioscopic examinations;
- Rates of ocular adverse events (intraoperative, postoperative);

The counts and percentages of eyes will be summarized for each adverse event. For each reported adverse event, the percentage of eyes (and the corresponding two-sided 95% confidence interval around the difference in rate per binomial distribution) reported with the safety event will be provided.

The primary analysis is the comparison of all adverse events between the investigational device and control groups through 12 months of follow-up.

^{iv} Does not include use in the perioperative period

^v If the study subject fails to remember not to use ocular hypotensive medication for the study eye per the required washout period prior to this visit, they can be re instructed to washout and return for a 12 month washout IOP visit as long as it falls within the specified visit window.

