5.2 Pre-Market Submission

When all randomized subjects have either completed the 12-month follow-up examination or have discontinued from the study, the data will be analyzed based on this Statistical Analysis Plan for a premarket FDA submission.

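### SAP 9.5.1 plans per-arm adverse-event intervals on all available data, not the between-arm 12-month comparison that Protocol 6.2 names as the primary safety analysis

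*SAP*

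**What the plan says.** Protocol 6.2 (Safety Endpoints) fixes the contrast and the time window: "The primary analysis is the comparison of all adverse events between the investigational device and control groups through 12 months of follow-up". For each event it also asks for the percentage of eyes and "the corresponding two-sided 95% confidence interval around the difference in rate per binomial distribution".

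SAP 9.5.1 (Adverse Event) says: "The number and the percent of subjects reporting at least 1 adverse event of a given type will be summarized by study group". The interval comes next: "The corresponding 95% confidence interval of the percentage will be calculated by binomial distribution". The rest of 9.5.1 gives event counts, events per subject, and severity and relationship summaries, all by group.

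SAP 9.5 sets the data window: "All safety analyses will be performed on the Safety population based on all available data". SAP 4.2 lists the safety outcomes without a contrast or a window.

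On timing, SAP 5.2 triggers the premarket analysis as follows: "When all randomized subjects have either completed the 12-month follow-up examination or have discontinued from the study". The Study Duration row of the protocol synopsis has a similar milestone, "The primary safety and effectiveness endpoints will be evaluated when each study subject has a minimum of 12 months" of follow-up, and then has all subjects followed to 24 months.

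**The concern.** The SAP governs the reports: Protocol 12.0 refers to it for the analysis detail, and SAP 5.2 and 5.3 say the data will be analysed according to it. Its adverse-event section departs from Protocol 6.2 in two ways. The interval describes one arm's percentage instead of the difference between arms. The data window is whatever has accumulated instead of the first 12 months.

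Two things are at stake. First, a reader given two per-arm intervals will tend to compare them by eye, and overlapping intervals can hide a difference whose own interval excludes zero. Second, a percentage over unequal follow-up is not a 12-month rate. If the interval method and the cut-off are left open, they may also be settled after the adverse-event data have been seen.

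**Working it through.** **Text comparison**

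| Item | Protocol 6.2 | SAP 9.5 and 9.5.1 |
|---|---|---|
| Quantity | Difference in rate between groups | Percentage within each group |
| Interval | Two-sided 95% CI for the difference | 95% binomial CI for the percentage |
| Window | Through 12 months | All available data |

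The protocol counts eyes and the SAP counts subjects. These are the same, because only one eye per subject is enrolled.

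No other SAP section supplies the missing analysis. SAP 8.1 gives general significance levels and optional exact intervals for point estimates. SAP 9.4.2 does specify a CI for a difference in proportions, but only for the responder endpoint. The blacked-out areas lie within section 9.4 (effectiveness). Sections 9.5 to 9.5.3 read without a gap, so redaction does not explain the omission.

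**Illustration: per-arm intervals against the interval for the difference**

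The documents state no safety sample size, margin or adverse-event rate, so there is no safety figure to reproduce. The counts below are assumed. The arm size is the 149 per arm of SAP 3.0 and 6.0 (134 ÷ 0.90 = 148.9, rounded up to 149).

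Formulas, with x₁ and x₂ events among n = 149 per arm, p = x/n and d = p₁ − p₂:

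- Exact per-arm (Clopper-Pearson) limits: lower = Beta(0.025; x, n − x + 1), upper = Beta(0.975; x + 1, n − x).
- Wald interval: d ± 1.96 × √[p₁(1 − p₁)/n + p₂(1 − p₂)/n].
- Newcombe interval: Wilson limits (l, u) for each arm, then d − √[(p₁ − l₁)² + (u₂ − p₂)²] to d + √[(u₁ − p₁)² + (p₂ − l₂)²].
- Score interval: all values of the difference that the score test (variance estimated under that difference) does not reject at two-sided 5%.

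Wald for 15 v 5: p₁ = 15/149 = 0.1007 and p₂ = 5/149 = 0.0336, so d = 0.0671. The standard error is √(0.1007 × 0.8993/149 + 0.0336 × 0.9664/149) = 0.0287. Then 6.71 ± 1.96 × 2.87 gives 1.1 to 12.3 points.

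| Assumed counts | Exact CI, first arm | Exact CI, second arm | Difference (points) | Wald | Newcombe | Score |
|---|---|---|---|---|---|---|
| 15 v 5 | 5.7% to 16.1% | 1.1% to 7.7% | 6.7 | 1.1 to 12.3 | 1.0 to 12.9 | 1.1 to 13.0 |
| 15 v 6 | 5.7% to 16.1% | 1.5% to 8.6% | 6.0 | 0.3 to 11.8 | 0.1 to 12.3 | 0.2 to 12.4 |
| 22 v 11 | 9.5% to 21.5% | 3.7% to 12.8% | 7.4 | 0.3 to 14.5 | 0.2 to 14.7 | 0.3 to 14.8 |

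The score upper limits in the first and third rows come out 0.1 lower (12.9 and 14.7) in one standard package. The lower limits agree. In every row the per-arm intervals overlap while all three intervals for the difference exclude zero.

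**Follow-up at the premarket cut**

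SAP 5.2 sets when the analysis is run, not which events count. A subject treated A months before the last subject has min(12 + A, 24) months of follow-up at that point. No accrual period is stated. If accrual were uniform over A months (A up to 12), mean follow-up among subjects still in the study would be 12 + A/2: 12 months at A = 0, 15 at A = 6 and 18 at A = 12. Some spread is certain, because Month 1 data from the initial phase must be submitted before enrolment can expand.

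**The case against.** Much of the opposing case has force.

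- **No conclusion turns on the missing interval.** The objective is safety and effectiveness in support of the indication statement. The only formal hypotheses are for effectiveness (SAP 4.1.1 and 4.1.2). A reader might infer that the trial has a comparative-safety aim that the SAP leaves untested. The documents do not support that: they give safety no hypothesis, margin, alpha, power or success criterion.
- **The SAP does not withdraw the protocol's comparison.** Protocol 6.2 remains in force, and a difference can be computed from by-group counts. This stands, but only in part: the planned counts have no 12-month cut, so the planned table alone does not give the protocol's quantity.
- **The protocol's own timing wording is loose.** The synopsis speaks of a minimum of 12 months, which allows longer follow-up for some subjects. Protocol 6.2 is the more specific text, so the cut-off still needs to be stated.
- **Mixed follow-up need not bias the comparison.** A reader might infer that it does. Allocation is 1:1, stratified by site and prior SLT in SAP 3.0, so calendar-driven follow-up should be similar between arms. The effect is on the time frame to which the percentages refer.
- **The counts are assumed.** They show how the intervals behave and say nothing about either procedure's likely event rates.
- **Many intervals without multiplicity control will sometimes exclude zero by chance.** This is correct and has to be dealt with in the fix.

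**Conclusion.** The concern holds as a mismatch between the two documents. The SAP's stated interval and data window both differ from those of Protocol 6.2, and the SAP as written would not produce the protocol's primary safety table. Nothing in the SAP's general sections, its timing rule or the redactions closes the gap.

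The size can only be illustrated. At 149 per arm with assumed counts, differences of about 6 to 7 points can have an interval that excludes zero while the exact per-arm intervals overlap. At the premarket cut, follow-up would range from 12 to at most 24 months, by an amount the documents do not let one calculate.

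This is an estimation analysis. The mismatch does not touch the sample size, the effectiveness tests or any success rule, and it is not evidence that the comparison between arms would be biased. It should be corrected before database lock, but it does not threaten the trial's main conclusion.

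**What to change.** Amend SAP 9.5.1, with a matching line in 9.5:

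1. For each adverse event type, and for any ocular adverse event, report the VISCO360 minus SLT difference in percentage with a two-sided 95% CI. Name one method for a difference of binomial proportions in advance. The protocol says only that the interval is binomial, so the choice is open, but it should be made before the data are seen.
2. Make events through the Month 12 visit the primary safety table. State which visit closes the window for subjects who have a separate Month 12 washout visit.
3. Keep the all-available-data tables, with the per-arm intervals, as supportive.
4. State that the intervals for the differences are descriptive, with no multiplicity control and no success criterion.

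The cost is SAP wording, a cut-off rule and one extra table column. No new data are needed, and SAP 1.0 allows amendment before database lock. The downside is some chance exclusions of zero: with, say, 20 event types and no true differences, nominal 95% intervals would give about 20 × 0.05 = 1. The descriptive label is there for that reason.
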